### 2.5.2 Statistical Analysis

The primary assessment of RBC transfusion efficacy is post transfusion survival. Data from RBC recovery at 2-4 hours, 1 month and 2 months after each transfusion will be evaluated using mixed effect model (with restricted maximum likelihood variance estimator and bootstrapping) to calculate the effect of time, genetic group and their interaction on RBC survival. RBC recovery at each time point will be performed using the equation below.

$$\text{Percent survival (\%)} = \frac{\text{BioRBCs in circulation at } T_y \text{ (} 1 \leq y \leq 120 \text{ days)}}{\text{Baseline BioRBCs in circulation at } T_0 \text{ (20 min following RBC infusion)}} * 100$$

Secondary endpoints: The equation above will be used to define the 2-4hours post transfusion survival of BioRBCs. The other endpoints test for changes in RBC predisposition to hemolysis in cold storage by quantifying the rates of storage, osmotic, mechanical and oxidative hemolysis and the formation of RBC membrane-derived microvesicles. A sample size of 8 samples would detect a 10% difference in our assays' outputs with a power of 85%. We will use commercial software for statistical analyses (STATA version 15.0, StataCorp., College Station, Texas, USA). We will use mixed effect model (with restricted maximum likelihood variance estimator and bootstrapping) to calculate the effect of time, genetic group and their interaction on RBC survival. Normality tests will help to determine the appropriate transformation of outcome data. We will also use nonlinear term of time in these models (if applicable). We will use marginal test (from the primary models) to assess the effect of genetic group on 60-days and 2-4hours RBC survival separately. As a confirmatory analysis, Wilcoxon signed rank test will determine the differences between two groups for 60-days and 2-4 hours survival rate as well. The hypotheses will be tested primarily in old blood. A separate analysis will be performed in fresh blood transfusion as well. All P value <0.05 will be reported as statistically significant.

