## 2.5 STATISTICAL ANALYSIS

### 2.5.1 Sample Size Determination

In healthy volunteers, the mean (SD) of 30 and 60-days RBC biotin recovery rate is 75% (12.5%) and 50% (10%) (calculated from 24-hour 100% recovery value), respectively. For our first study, evaluating patients with the sickle cell trait SNP, we expect SCD trait to reduce 30 and 60-day recovery to 62% and 25%. A sample size of 15 subjects with sickle cell trait (HbAS) and 20 control African American subjects (HbAA; 10 males and 10 females) would provide 84% power to detect a difference of 13% (SD =12.5%) for 30 days and a power of >95% to detect a difference of 25% (SD = 12.5%) for 60 days RBC recovery rate between AS and AA. This sample size has at least 80% power to detect the interaction between time and genetic group as measure of different recovery rate. We will also recruit an additional 20 Caucasian control (HbAA, 10 males and 10 females) to gain power for testing the effect of other RBC mutations identified in our genome-wide association studies of blood donors (NHLBI RBC-Omics). We will use explanatory analysis for the evaluation of post transfusion recovery of RBCs from subjects with rare variants (<10% of the population) due to a projected small number of subjects carrying such mutations. All 40 control subjects will be tested and selected to not have any of the SNPs that we are studying (listed below).

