This power calculations informs our other planned studies that will compare up to 7 additional single nucleotide polymorphisms (SNPs) patient groups of 15 each, compared with our control groups without the SNPs (n=20 race and gender matched). Successful enrollment of the sickle trait and 7 SNP groups would be 120 total subjects. The eight genetic mutations that we will evaluate may include sickle cell trait (AS), and single nucleotide polymorphisms (SNPs) in ankyrin 1 (ANK1), glucose-6-phosphate dehydrogenase X-linked (G6PD), piezo-type mechanosensitive ion channel component 1 (PIEZ01), spectrin alpha (SPTA), extended synaptotagmin-like protein 2 (ESYT2), Myo9b and SEC14. We may identify additional SNPs as our analysis of the REDS-III GWAS study advances that could replace one of these SNP groups and/or we identify additional non-synonymous SNPs that are associated with susceptibility to hemolysis of stored red blood cells. In addition, we will evaluate 15 subjects on testosterone replacement therapy with 20 controls that are gender and race matched that are not on testosterone replacement therapy.

Each study will be conducted as an independent analysis of 15 subjects with the SNP and 20 race and gender matched subjects without the SNP using power calculations estimated from the SCD trait example above.

**Biotin infusion study:** The study team will target 70 evaluable subjects. The study team will approach 86 subjects with 90% expected to agree to yield 78 subjects who will sign the biotin infusion consent. The study team expects 90% of these subjects to complete the biotin infusion study yielding the target 70 evaluable subjects. The biotin infusion subjects include 20 Whites, 20 African American without sickle cell trait, 15 African Americans with sickle cell trait, and 15 males on testosterone. In addition, 20 subjects with SNPs from the REDS-III RBC-OMICS study will be included for a total of 98 subjects to sign the biotin infusion consent and yield approximately 90 subjects who complete the study.

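### The primary tests use an unspecified bootstrap with 15 versus 20 subjects and no small-sample correction, so the 5% level is not assured, least of all for small SNP groups

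*Combined protocol and SAP*

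**What the plan says.** Section 2.5.2 (Statistical Analysis) specifies a "mixed effect model (with restricted maximum likelihood variance estimator and bootstrapping" for the effects of time, genetic group and their interaction on red cell survival. The group tests at 60 days and at 2-4 hours are taken from this model. The decision rule is "All P value <0.05 will be reported as statistically significant". The section gives no bootstrap type, resampling unit, stratification, number of replicates, interval method or small-sample reference distribution.

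Section 2.5.1 (Sample Size Determination) sizes each comparison at "15 subjects with the SNP and 20 race and gender matched subjects without the SNP" and plans up to seven SNP groups of 15 beyond sickle cell trait. For the infusion study it then says "In addition, 20 subjects with SNPs from the REDS-III RBC-OMICS study will be included". The paragraph on the REDS-III RBC-OMICs study confirms that these 20 are the only ones among its 105 SNP carriers who also sign the infusion consent. Section 2.5.1 calls the analysis of variants found in under 10% of the population explanatory, because few carriers are expected. It names no test for that analysis and does not say whether the 0.05 rule applies to it.

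**The concern.** Resampling n subjects with replacement understates the variance of their mean by the factor (n-1)/n. A percentile interval, or a bootstrap standard error with a 1.96 cut-off, also makes no allowance for estimating the variance from few subjects. Both effects make intervals too narrow and rejections too frequent. They are modest at 15 versus 20 and large when one group has only a handful of subjects.

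At stake is the error rate behind any claim that a donor genotype changes red cell recovery, before any question of testing several SNPs. The SNP groups with fewest carriers would be affected most.

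**Working it through.** **1. The plan's own figure.** Inputs from section 2.5.1: difference 13 points, SD 12.5, 15 and 20 subjects. Sidedness is not stated; two-sided 0.05 is assumed.

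Noncentrality = 13 / (12.5 × √(1/15 + 1/20)) = 13 / 4.27 = 3.04. A two-sided t test on 33 df then has power 84.0%, which matches "would provide 84% power to detect a difference of 13% (SD =12.5%) for 30 days". A normal approximation gives 86.1% and a one-sided t test 90.9%. At 60 days (25 points, SD 12.5) the t test gives 99.99%, consistent with the stated figure above 95%. The stated power therefore matches a t reference, which section 2.5.2 does not carry into the analysis.

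**2. Why the usual bootstrap is too narrow.** With complete data and categorical time, the 60-day contrast is a difference of two means. With many replicates and equal SDs, the bootstrap variance stratified by group is proportional to (n1-1)/n1² + (n2-1)/n2², against 1/n1 + 1/n2.

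- 15 v 20: 14/225 + 19/400 = 0.1097 against 0.1167. Variance ratio 0.940, SE ratio 0.970. The effective cut-off is 1.96 × 0.970 = 1.90, where t on 33 df needs 2.03.
- 3 v 20: 2/9 + 19/400 = 0.2697 against 0.3833. Variance ratio 0.704, SE ratio 0.839. The effective cut-off is 1.96 × 0.839 = 1.64, where t on 21 df needs 2.08. The carrier variance also rests on three values alone, which adds to the excess.

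**3. Simulated type I error at one time point** (normal errors, equal SDs, true null, nominal 5%):

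| Method | 15 v 20 | 3 v 20 | 3 v 40 |
|---|---|---|---|
| Stratified bootstrap SE, 1.96 cut-off | 6.7% | 18.4% | 21.0% |
| Stratified percentile interval | 6.8% | 18.7% | 20.4% |
| Unstratified bootstrap SE, 1.96 cut-off | 6.0% | 15.3% | 16.2% |
| Unstratified percentile interval | 6.4% | 16.1% | 17.5% |
| Residual bootstrap SE, 1.96 cut-off | 6.2% | 8.0% | 5.2% |
| Bootstrap-t | 4.8% | 7.1% | 6.8% |
| Pooled SE, 1.96 cut-off, no bootstrap | 5.8% | 6.4% | 5.9% |
| Pooled SE, t reference | 5.0% | 5.0% | 5.2% |

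The first and last two rows use 100,000 trials (Monte Carlo SE about 0.1 point). The others use 3,000 trials with 600 resamples (about 0.4-0.7 point). The first method gives 7.5% with 10 carriers, 11.6% with five and 13.8% with four, each against 20 controls.

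At 15 v 20 the excess is 6.7 - 5.0 = 1.7 points. Of this, 5.8 - 5.0 = 0.8 arises with no bootstrap at all, from the normal reference.

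**4. Time-by-group test.** Three time points, SDs 5 (assumed), 12.5 and 10, within-subject correlation 0.5 (assumed), 1,500 trials with 400 subject-level resamples (Monte Carlo SE about 0.6-1.3 points). At 15 v 20 the 60-day test rejects in 6.4-6.5% and the 2-df time-by-group test in 8.0-8.8%. With three carriers the 2-df test rejects in 31-34% against 20 controls and 38-41% against 40.

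**5. Unequal SDs.** Section 2.5.1 gives a control SD of 10 at 60 days but uses 12.5 in the power statement. With 12.5 in carriers and 10 in controls, a pooled t test rejects in 5.8% at 15 v 20, 9.4% at 3 v 20 and 10.4% at 3 v 40. Over normal and skewed errors and both orderings of these SDs, the usual bootstrap gives 6.4-9.2% at 15 v 20 against roughly 4-6% for the t reference, and 17-22% against 2-10% at 3 v 20.

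**6. Carriers available.** Seven groups of 15 need 7 × 15 = 105 carriers; the infusion study includes 20. Unless carriers overlap heavily, at most one SNP reaches 15, leaving 20 - 15 = 5 for the rest. An equal split over seven gives 20/7 = 2.9 each.

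**The case against.** The strongest reply is that section 2.5.2 names no bootstrap, so the rates above belong to methods chosen for the check. Bootstrap-t holds 4.8% at 15 v 20. With three carriers, a residual bootstrap or bootstrap-t gives about 5-8%, not 18-19%. This stands, and it makes every figure conditional.

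The excess at the stated 15 v 20 is also only 1-2 points for the 60-day test, about half of it unrelated to bootstrapping, in a study that section 2.1 calls a pilot. This stands too.

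Three carriers per SNP is nowhere stated. It assumes that all seven SNPs are infused, split equally and analysed separately. The 20 carriers could be concentrated in one or two SNPs, or pooled through the high-risk and low-risk donor profile described in section 2.2.1. That is fair, but five carriers already give 11.6%, and any separate analysis of several SNPs leaves most groups far below 15.

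Two further replies help less. Rare variants are called explanatory, but nothing clearly exempts them from the 0.05 rule. The confirmatory Wilcoxon test does not depend on the bootstrap, but it is specified as a signed rank test, which needs pairs that 15 v 20 separate subjects do not supply.

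Finally, the exact 5% for the t reference follows from simulating normal data with equal SDs. With unequal SDs it does not hold in tiny groups (step 5). It still came closer to 5% than the usual bootstrap in the settings compared there.

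**Conclusion.** The point holds conditionally: the plan does not assure its 5% level. Under the usual subject-level bootstrap, normal errors and equal SDs, the 60-day test at 15 v 20 runs at about 6-7%. The 2-df time-by-group test runs at about 8-9% under the assumed correlation of 0.5. Where SNP groups are analysed separately, a stratified bootstrap runs at about 11-12% with five carriers and 18-19% with three against 20 controls; the three-carrier case rests on an equal split over seven SNPs.

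A reader might infer that the plan has been shown to miss its 5% level, or that nearly one SNP test in five will be a false positive. The documents support neither. They leave the bootstrap open, some versions hold close to 5% at 15 v 20, and they never state three carriers per SNP. What they do show is a primary analysis whose error rate depends on an unmade choice, with no small-sample correction.

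**What to change.** In section 2.5.2:

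- Take p-values and confidence intervals for the group and time-by-group effects from the REML model with a small-sample degrees-of-freedom correction, such as Kenward-Roger.
- For SNP groups too small to support the model, use a permutation test of the group label, with the minimum group size fixed in advance. Three carriers against 20 controls allow 1,771 allocations, enough to test at 0.05. State that this test and the t reference both assume similar variances, and that the t reference can reach about 10% with three carriers if the SDs are 12.5 and 10.
- Keep the subject-level bootstrap as a sensitivity analysis, with its type, stratification, replicates and interval method specified.
- State that rare-variant analyses are exploratory and are not declared significant at P<0.05.

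Section 2.5.1 should also say how many carriers of each SNP will be infused, so that the reader knows which analysis applies.

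The cost is SAP wording and slightly wider intervals: at 15 v 20, about 2.03 / 1.90 = 1.07 times as wide as with the bootstrap SE and a normal cut-off. The stated 84% power is unaffected, because it already matches a t reference.

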#### Visit 5 (Day 32-41)

This visit will be scheduled approximately a little over one month (ranges between 32-41 days) after completion of 1st transfusion in MUH-CTRC.

- Blood draw to test antibodies to BioRBCs. If anti-BioRBC antibodies are detected following 1st transfusion, the subject will be withdrawn from the study. A negative test result must be confirmed prior to proceeding with 2nd transfusion.
- Blood draw for Type and Cross (ABO/Rh type and antibody screen) prior to transfusion
- AE assessment

Total blood volume drawn will be about 1 tablespoon (approximately 10 mls).

Visit 6 (Day 35-42) This visit will be scheduled between approximately 35-42 days following blood donation in MUH-CTRC. A “Physician’s Processing Request form” will be sent to the HSCLab staff via the UPMC secure email system. This form will have the subject’s private health information and the study ID number that is reviewed and signed/dated by the PI or Co-I in this study. In order for the blood to be released from HSCLab to CTRC, HSCLab will need this form. The Vitalant form, “Patient Identification Form” that is sent to HSCLab by the study team via the UPMC secure email system will contain the subject’s private health information and study ID

number. In order for the blood to be released from Vitalant to HSCLab on the day of biotinylation, Vitalant will need this form.

- Brief physical examination to include vital signs (Temp, HR, RR, BP, pulse ox)
- Review medical history and demographics
- Urine pregnancy test in women of childbearing potential
- Blood draw for whole blood sample will be sent to Wake Forest University
- Blood draw for clinical lab testing (CBC)
- Blood draw prior to transfusion to detect presence of BioRBCs. Results not needed to proceed with the study.
- Transfuse 150 mL of 35-42 days old biotin-labeled RBCs
- Obtain the subject's leftover BioRBCs in IV line/unit of blood for storage and stress hemolysis
- Vital signs (Temp, HR, RR, BP, pulse ox) approximately every 15 minutes during the transfusion and approximately 15 minutes post transfusion
- Blood draw approximately 2-4 hours post transfusion to determine baseline for 35-42 days old BioRBCs.
- AE assessment
- Given meal

Total blood volume drawn will be about 2 tablespoons (approximately 14 mls).

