#### **2.3.1. Investigational Product Preparation and Dispensing**

The packed RBCs will be biotin-labeled under sterile conditions by trained personnel at the UPMC Hematopoietic Stem Cell Laboratory (HSCLab), an International Organization for Standardization Class 7 (ISO7) Current Good Manufacturing Practice (cGMP) compliant facility. The HSCLab has a Master file on file with the FDA that is cross referenced by this protocol. Preparation of the biotin solution and filter sterilization occurs immediately before addition to the autologous red blood cell sample, which is handled under sterile conditions. The sterile biotin reagent and autologous RBCs are combined at a constant rate and are incubated at room temperature for 30 minutes to allow biotin to bind to the surface of the RBC membrane. After the incubation period, the product is washed and re-suspended in saline with 5% human serum albumin. A BioRBC sample is removed by sterile technique for release testing. Release criteria include a final RBC packed cell volume  $\geq 25 \text{ mL}$  and total endotoxin content of  $< 5 \text{ EU/kg}$  recipient actual body weight. The product will be withheld if either of these criteria is not met. Additional product quality testing will include quantitative flow cytometry to determine the actual dose of biotin in each product, and pre- and post labeling 14 day aerobic, anaerobic and fungal sterility cultures.

The biotinylated autologous RBCs will be provided in 300 mL transfer bags for infusion, at a volume of  $\sim 150 \text{ mL}$  and a hematocrit of approximately 35% to 40%. The HSCLab is (Foundation for the Accreditation of Cellular Therapy (FACT) accredited and uses International Society of Blood Transfusion (ISBT) 128 Standard Terminology for Blood, Cellular Therapy, and Tissue

Product Descriptions labeling and packaging, according to Good Clinical Practice and regulatory requirements. HSCLab will dispense the BioRBC product upon receiving a signed and dated physician's processing request form. The HSCLab will maintain accurate records of investigational products including subject dispensing, product destruction and documentation of adequate storage of investigational products.

Further details on investigational product preparation and dispensing are provided in a separate laboratory standard operating procedure.

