### **2.3.2. Administration of Investigational Product**

BioRBCs will be administered intravenously on two separate occasions (5-7 and 35-42 days following donation). BioRBCs will be transfused at a rate of 100-150 mL/hr. This range will allow us to reduce infusion rate if recipient complains of any discomfort or pain. Recipient vitals will be taken at baseline and approximately every 15 minutes during the infusion and then approximately 15 minutes after the infusion ends by qualified personnel at the Clinical Translational Research Center (CTRC) of UPMC Montefiore Hospital.

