### **2.3.3. Dose Selection**

Experience with biotin labeling method to study RBC survival in humans is expanding. Biotinylated RBCs (BioRBCs) were first used to study RBC survival in rabbits in 1987. Since then, the use of BioRBCs has successfully been expanded to human studies evaluating RBC 24-hour recovery and lifespan. Investigators have used BioRBCs to study RBC volume and survival in healthy adults. BioRBCs have also been used in patients with sickle cell disease to study autologous RBC survival and post-infusion membrane changes, and it is currently being used to study both autologous and allogeneic RBC survival in neonates in the intensive care unit. The primary safety concern in using the BioRBC method in humans is the potential formation of antibodies against the BioRBCs. The formation of anti-BioRBC antibodies was observed in 3 subjects out of 20 adults studied (15%). The anti-BioRBC antibodies appeared 4-5 months after the infusion of BioRBCs, reacted only against BioRBCs (i.e. antibodies did not behave as autoantibodies), did not affect BioRBC 24-hour recovery or survival, and were transient in nature (i.e. anti-BioRBC antibody activity disappeared within 1-4 months after initial detection).

Biotin has also been directly administered to healthy adults both orally and intravenously with daily oral doses being as high as 2000 µg and IV doses as high as 4500 µg without any reported adverse effects. In this study, subjects will receive a total biotin dose of approximately 0.2 µg/ml (27.5 ug biotin) during the first transfusion visit and 0.04 µg/ml biotin (5.5 ug of biotin) during the second transfusion visit.

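### Recovery is scored only against labelled cells still circulating after the infusion, so a genotype effect on clearance before the baseline sample is hidden; cells infused should be added as a second denominator

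*Combined protocol and SAP*

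**What the plan says.** Section 2.5.2 gives one formula, percent survival. On its use it says "RBC recovery at each time point will be performed using the equation below". The numerator is labelled cells in circulation at a later time, and the denominator is labelled cells in circulation at T0, defined as "20 min following RBC infusion". The same ratio serves the early secondary endpoint: "The equation above will be used to define the 2-4hours post transfusion survival of BioRBCs".

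Two other baselines appear. The Visit 6 procedures (section 2.2.2) list "Blood draw approximately 2-4 hours post transfusion to determine baseline for 35-42 days old BioRBCs". Section 2.5.1 expresses its planning values relative to a 24-hour value taken as 100%. Both are again circulating cells. Nowhere is the number of cells infused used as a denominator.

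On administration, section 2.3.2 says "BioRBCs will be transfused at a rate of 100-150 mL/hr", and Visit 6 says "Transfuse 150 mL of 35-42 days old biotin-labeled RBCs".

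The content of each product is nevertheless determined. Section 2.3.1 states "Release criteria include a final RBC packed cell volume" (at least 25 mL), and the dose formula in section 2.3 multiplies biotin per cell by total red cells.

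**The concern.** The primary objective and endpoint concern recovery of stored cells after transfusion, and the rationale in the synopsis is hemolysis and reduced survival after transfusion of aged cells. A ratio of two post-infusion samples cannot count cells that have already gone by the first of them. Moving the baseline among 20 minutes, 2-4 hours and 24 hours does not help, because each is taken after the infusion.

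The stake is interpretation. If a variant acts mainly by making stored cells clear soon after transfusion, the planned endpoint could show little or no difference. The planned correlations between in vitro hemolysis and recovery (section 2.4) would lack that part of the outcome as well. A null result could not separate no effect on clearance from an effect that was over before the first sample.

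**Working it through.** **1. The plan's own figure.** Inputs from section 2.5.1: 15 carriers, 20 controls, control survival 75% (30 days) and 50% (60 days), carrier survival 62% and 25%, SD 12.5 points. Standard error = 12.5 × √(1/20 + 1/15) = 4.27; 13/4.27 = 3.04 on 33 degrees of freedom. A two-sided t-test at 0.05 gives power of 84.0% (stated: 84%). For 25 points it gives 99.99% (stated: above 95%). Both are reproduced. These inputs are relative to circulating cells, so the plan and its power calculation share the same kind of scale.

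**2. Time before baseline.** 150 mL ÷ 150 mL/hr = 60 min; 150 ÷ 100 = 90 min. At 20 minutes after the end of infusion, the first cells have circulated for 80-110 minutes.

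**3. Relation between the two scales.** Let e be the fraction of infused cells lost before baseline and S the survival the plan measures. Recovery of infused cells = (1 − e) × S. Write c for control and k for carrier.

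- Ratio: [(1 − e_k)/(1 − e_c)] × (S_k/S_c). If e_k > e_c, the first factor is below 1. The plan drops that factor, so its ratio lies nearer 1.
- Difference: the plan understates it only if e_k × S_k > e_c × S_c, that is, if e_k/e_c > S_c/S_k. With the plan's figures the thresholds are 75/62 = 1.21 at 30 days and 50/25 = 2.0 at 60 days.

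The document gives no value for e, so the values below are assumptions. The plan's differences are 13 points (ratio 0.827) at 30 days and 25 points (ratio 0.500) at 60 days.

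| Early loss, control v carrier | Infused-based difference, 30 d | Infused-based difference, 60 d |
|---|---|---|
| 10% v 10% | 11.7 | 22.5 |
| 10% v 15% | 14.8 | 23.8 |
| 20% v 30% | 16.6 | 22.5 |
| 10% v 20% | 17.9 | 25.0 |
| 5% v 15% | 18.6 | 26.3 |
| 10% v 30% | 24.1 | 27.5 |

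Example, 10% v 20%: at 30 days 0.9 × 75 − 0.8 × 62 = 17.9 points (ratio 0.735); at 60 days 0.9 × 50 − 0.8 × 25 = 25.0 points (ratio 0.444).

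**4. Effect confined to early clearance.** Take S equal in both groups (100, 75 and 50% at 2-4 hours, 30 and 60 days) and losses of 10% v 20%. The infused-based difference is 0.10 × S = 10, 7.5 and 5 points. The plan's equation gives 0 at all three.

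**5. Gradual clearance.** Assume 10% v 20% non-viable cells that clear with a half-life of 0.5-2 hours from a 60-90 minute constant infusion. The share of non-viable cells still present d hours after an infusion of D hours is [(1 − exp(−kD))/(kD)] × exp(−kd), where here k = ln 2/half-life.

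- With identical viable cells, the difference per infused cell is 7.0-9.9 points at 3 hours and 5.0 at 60 days. Against a 20-minute baseline it reads 3.3-5.5 and 1.7-4.1. Against a 3-hour baseline it reads 0 and 0.05-1.9.
- With the plan's survival figures applied to the viable cells, and baselines from 20 minutes to 4 hours, the 30-day difference falls from 17.9 to 13.0-17.0. The 60-day difference, 25.0 per infused cell, reads 25.0-25.15.

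**6. Baseline against schedule.** Neither Visit 3, Visit 6 nor Appendix A lists a 20-minute draw; the first post-infusion sample is at 2-4 hours. If that sample is T0, 2-4 hour survival is X/X = 100% for every subject, and the marginal genotype test at 2-4 hours in section 2.5.2 has no variation to work on.

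**The case against.** A reader might infer that the equation always shrinks the carrier-control difference. The plan's own figures do not support that. On the percentage-point scale, the 60-day difference is unchanged at 10% v 20% early loss, and reads larger than the infused-based one at 10% v 15% (25.0 against 23.8) or 20% v 30% (25.0 against 22.5). Only the pull of the ratio toward 1 follows whenever carriers lose more early.

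The size is also open. No early-loss fraction or clearance half-life is given, the synopsis rationale says nothing about speed, and the hypothesis concerns recovery over 60 days, with the expected gap growing from 13 to 25 points. The formula is openly labelled percent survival, and survival relative to circulating cells is a legitimate quantity. Storage, osmotic, mechanical and oxidative hemolysis and microvesicles are separate endpoints, so storage damage would not go unexamined. All of this stands. It limits the claim about direction and size, but does not restore sight of cells lost before baseline.

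Two practical objections also stand. Some product is left in the line or bag and kept for assays, and its volume is not stated to be recorded, so product content is not the same as cells infused. A within-subject stored/fresh ratio would avoid estimating red-cell volume, but it cancels any genotype effect common to fresh and stored cells, and the objective covers both.

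**Conclusion.** The concern holds in a conditional form. Every baseline in the document is circulating cells after a 60-90 minute infusion, so clearance before baseline cannot be seen. When carriers lose more cells early, the carrier/control ratio is drawn toward 1. The absolute difference is understated at 30 days if carrier loss exceeds 1.21 times control loss, and at 60 days only above 2.0 times. Otherwise it is unchanged or overstated. These thresholds rest on the survival figures in section 2.5.1.

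In the limiting case, with all the effect before baseline and an assumed 10% v 20% loss, 10, 7.5 and 5 points read as zero. The one consequence that needs no assumption about loss is that a 2-4 hour baseline makes the 2-4 hour value 100% by construction.

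This does not invalidate the survival analysis or its stated power. It limits what a null result can mean, and much of the information needed to address it is already collected.

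**What to change.** In section 2.5.2:

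1. Keep the survival curve. Name one T0 that corresponds to a scheduled draw, and reconcile 20 minutes, 2-4 hours and 24 hours wherever they appear. If T0 is the 2-4 hour sample, remove the 2-4 hour test on that scale.
2. Add a secondary endpoint for each product, recovery of infused cells at 2-4 hours: labelled fraction × estimated red-cell volume ÷ (product packed red-cell volume − packed red-cell volume in the leftover). Estimate red-cell volume from height and weight (Visit 1) and the CBCs at Visits 3 and 6.
3. Record the leftover volume at each infusion so that it can be subtracted.
4. Report this endpoint separately for fresh and stored products. Use the within-subject stored/fresh ratio only as support.

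Cost: one extra recorded item per infusion, plus analysis work; the remaining inputs are already obtained. The downside is precision. Red-cell volume is estimated, and errors in it and in product content add variance, so the new endpoint should remain secondary.
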